In Malaysia, there are no specific guideline for prediabetes individual and they are managed according to the latest Clinical Practice Guideline in Malaysia (MOH *et al.*, 2020). For prevention prediabetes to further develop to diabetes, lifestyle intervention such as weight loss (5-10% of initial body weight), regular physical activity (150 min/week), with dietary strategies including reduced calories and behavior modification are recommended in Clinical Practice Guideline in Malaysia (MOH *et al.*, 2020). A high fibre diet (20-30g/day with 5 to 7 servings/day) consisting of vegetables, fruits, legumes and whole grains is encouraged too (MDES, 2020). All the prediabetic individuals will be referred to dietitian and nurse educators for 6 months routine treatment, prior to T2DM diagnosis, determined by second-round of oral glucose tolerance test (OGTT) in 6-month period (MOH *et al.*, 2020). To the puzzlement of many diabetes researchers and clinicians, some of the prediabetes cases showed tremendous improvement in their blood sugar result, yet some of the prediabetes

individuals developed full-blown of T2DM with their blood sugar result higher than the normal range; despite all of them followed the same routine treatment from healthcare clinics. Perhaps, besides the usual routine treatment from Clinical Practice Guideline (MOH *et al.*, 2020) (weight management, physical activity advices and dietary modification); prediabetic individuals who able to improve their blood sugar result in 6-month period has particular meal-timing, compared to those has uncontrolled blood sugar result in 6-month period.

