1.1 Prediabetes

Prediabetes is defined as a condition in which people have higher than normal blood glucose levels but not high enough for a diagnosis of diabetes. Prediabetes prevalence is higher than that of diabetes in China and many of the Western Pacific region countries, this is true of many countries in Asia (IDF 2017). South Asian population also have a high prevalence of prediabetes and a more rapid progression to diabetes (IDF 2017). In Malaysia, National Health and Morbidity Survey (IPH 2019) found the prevalence of prediabetes was 8.9%. These prevalence were likely to be underestimates because diagnosis relied only on a single fasting blood sugar, history of physician diagnosis and information on medication (Nanditha et al. 2016). Globally, an estimated 318 million people had prediabetes in 2015, with a projected alarming increase to 482 million in 2040 (IDF 2015). Prediabetes is high-risk condition for diabetes and cardiovascular disease (Nanditha et al. 2016). Without appropriate interventions, 5.8%-18.3% of people with prediabetes develop diabetes yearly (Anothaisintawee et al. 2017). How to prevent the development of diabetes from prediabetes?

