Those who meet the inclusion criteria will be invited to participate in this study. Eligible participants shall meet all the following inclusion criteria.

- 1) Newly diagnosed prediabetic individuals who have been first seen by clinical dietitian registered under the Ministry of Health Malaysia.
- 2) Malaysian ≥ 18 years old.
- 3) Those who plan to continue prediabetes care at a community clinic in Melaka.
- 4) Those who can read, write and understand the Malay Language.

Participants who meet the following criteria will be excluded from continuing the study.

- 1) Night shift workers at least 3 times per week.
- 2) Known sleep disorder.
- 3) Pregnant Women.
- 4) Those on oral glucose-lowering medications, diabetes supplements, anticonvulsant medications or oral steroids currently or in the last month.
- 5) Those with prior explored to any information regarding time-of-eating/time-of-activity restriction.
- 6) Those with chronic kidney disease. They are excluded as current research lack of evidence to support the accuracy of using 24-hour continuous glucose monitoring system (CGMS) (Freestyle Libre Pro, Abbott, Germany).

Prediabetes and diabetes will be defined according to the latest Clinical Practice Guideline in Malaysia (WHO & IDF, 2006; ADA, 2020; MOH *et al.*, 2020). Diagnosis must be confirmed by measurement of venous plasma glucose (FBG and OGTT) or HbA1c level. Table 1 shows the diagnostic value for diabetes on plasma glucose. Table 2 shows the diagnostic values for prediabetes and diabetes based on OGTT. Table 3 shows the diagnostic values for prediabetes and diabetes based on HbA1c. All the tables are adapted from the Clinical Practice Guideline in Malaysia (WHO & IDF, 2006; ADA, 2020; MOH *et al.*, 2020).

Table 1 The diagnostic value for diabetes on plasma glucose

	Fasting	Random
Venous Plasma Glucose	≥ 7.0 mmol/L	≥ 11.1 mmol/L

In symptomatic individual, one abnormal glucose value is diagnostic.

In asymptomatic individual, 2 abnormal glucose value are required.

Table 2 The diagnostic values for prediabetes and diabetes based on OGTT

OGTT Plasma Glucose Values (mmol/L)		
Category	0 hour	2- hour
Normal	<6.1	<7.8
IFG	6.1-6.9	
IGT	-	7.8-11.0
DM	≥ 7.0	≥ 11.1

IFG= impaired fasting glucose; IGT=impaired glucose tolerance; DM=diabetes mellitus

Table 3 The diagnostic values for prediabetes and diabetes based on HbA1c

	Normal	Pre-diabetes	Diabetes
A1c	<5.6% (38mmol/mol)	5.6-6.2% (38-44 mmol/mol)	≥6.3% (45mmol/mol)

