research assistant using the following questionnaire including (1) Munich Chronotype Questionnaires (MCTQ) (Appendix D), (2) Pittsburgh Sleep Quality Index Questionnaire (PSQI) (Appendix H), (3) Harvard Light Exposure Questionnaire (HLEQ) (Appendix G), (4) International Physical Activity Questionnaire (IPAQ) (Appendix C) and (5) Chrononutrition Profile Questionnaire (CPQ) (Appendix I). Anthropometry measurements including body fat, height, body fat percentage, visceral fat, waist circumference and hip circumference will be measured. Participants are requested to fill up 3-days dietary record (3DDR) (2 weekdays and one weekend day) and the data will be collected in the next visit. Baseline reading of fasting plasma glucose (FPG, OGTT, liver function, and HbA1c) will be retrieved from medical records in the community clinic. Routine treatment will be provided as usual. To minimize the loss of follow-up, phone conversations will be made to ensure the 3-days dietary data is completed.

At the second visit (three months from the baseline), all participants are required to wear a CGMS sensor at the back of their upper arms to measure the 24 hours glucose fluctuation over 14 consecutive days. 3DDR will be given to participants to record their consecutive 3 days dietary record and will be returned after 14 days. After 14 days, participants will return the CGMS sensor at the community clinic. Or alternative way of CGMS sensor collection by an assistant at the participant's home. All questionnaires will be interviewed by a trained research assistant again. Anthropometry measurements including body fat, height, body fat percentage, visceral fat, waist circumference and hip circumference will be measured repeatedly.

At the third visit (six months from the first visit), for FBG, OGTT and HbA1c test, all the readings will be retrieved by the research assistant from the medical record to document the glycemic outcome. The participants will be interviewed by the trained research assistant during all clinic visits using similar questionnaires. All anthropometry measurements (body fat, height, body fat percentage, visceral fat, waist circumference and hip circumference) will be conducted again. 3DDR will be given to record their 3 days dietary intake again and the record progress will be followed up through phone. The original 3DDR will be collected at the routine appointment.

Sample size Calculation:

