The sample size is estimated using G*Power software version 3.1.9.4 (Erdfelder, Faul and Buchner, 1996). To determination of association between chrononutrition and glycemic control, the β -coefficient of 0.13 adopted from Sakai *et al.*, (2018), the power was set to 0.9 with 2 sided significance level and alpha error given 0.05, a total of 83 prediabetic adults expected in this study. To compensate for the non-responding and non-compliance during follow-up, a dropout rate of 50% will be considered, the total sample size required is 166 subjects in the study for 6 months.

Test Family: T Test

Statistical Test: Linear Multiple Regression Fixed Model, single regression coefficient

Tail(s): 2

Effect Size (β -coefficient): 0.13 (Sakai *et al.*, 2018)

α Error prob: 0.05

Power(1- β err prob): 0.90

[figure not shown]
Total Sample Size: 83 prediabetes individuals

50% dropout rate taken as consideration in study for 6 months follow up, total 166 prediabetes individuals shall be recruit in this study.

Dropout Rate:

$$= \frac{83}{1-0.5} = 166 \text{ prediabetic individuals}$$

Figure 3: Flow diagram of the study design

Participants will be undergoing OGTT, FBS and HbA1c tests after an overnight fast of 8-10 hours. This is a routine universal test for prediabetes/ diabetes diagnosis. Participants will be informed to eat their usual diet for three days prior to the test. The diagnostic value for diabetes on plasma glucose. the diagnostic values for prediabetes and diabetes based on OGTT, and the diagnostic values for prediabetes and diabetes based on HbA1c have been shown in Table 1, Table 2 and Table 3, respectively. Fasting blood sample will be taken for FBS and HbA1c tests. Subsequently, participants will be given 75-gram glucose water to drink within 5 minutes. Blood sample will be taken after 2 hours for glucose determination. Participants should rest throughout test with only plain water is allowed to drink. Figure 4 shows the procedure of OGTT. All the tests will be conducted in the healthcare clinic lab. Results will be traced from medical record.

Table 4: Summary of data collection and timeline

Data	Baseline	3 months	6 months
Sociodemographic			
Age	.	.	.
Date of Birth	.	.	.
Marital Status	.	.	.
Education Level	.	.	.
Occupation	.	.	.
Monthly Household Income	.	.	.
Health History	.	.	.
Smoking Habit	.	.	.
Supplementary Consumption	.	.	.
Anthropometry			
Weight	.	.	.
Height	.	.	.
Waist Circumference	.	.	.
Visceral Fat	.	.	.
Body Fat	.	.	.

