To investigate the association of physical activity (MET score and steps count), sedentary behaviors (MET score), sleep pattern (sleep duration), diet quality (distribution of total energy, carbohydrate, protein, and fat), and light exposure (timing responded to a different type of light) with glycemic outcome, the multivariable generalized linear model will be conducted. Meanwhile, anthropometric measures (body mass index, body fat, and waist circumference) will be categorized as either normal or overweight and obesity group, followed by using logistic regression to examine the association between anthropometry status and glycemic outcome (non-diabetes or diabetes). In addition, the glycemic outcome will be categorized into diabetes incidence (diabetes and non-diabetes) to determine the participants who had been diagnosed with diabetes at 6 months. A logistic regression test will be used to examine the association between early and late-night mealtime and diabetes incidence.

Quality control

To ensure that the database accurately reflects the data reported in the questionnaires, a pre-test will be carried out. The research assistant trained to conduct the study procedures included interviewing administrative questionnaires, CGMS device, 3 days dietary record, and pedometer. Monthly meetings are held with the principal

investigator to review study procedures and progression. A monthly report will be documented after the meeting.

Data monitoring and management

Participants are anonymized and assigned with a specific ID at study entry. To ensure accuracy and completeness of data entry, data are checked by identifying if there is any outlier or missing value. The data checking process is performed in the first, third and sixth month of the data collection, such that the experience gained can be used to train the research assistant for improvement. Paper documents are kept in a locked cabinet and electronic data are stored on password-protected computers which can only be accessed by research team members. All records will be kept for at least 5 years after completing the study. After 5 years, all papers will be shredded using an office shredder. Extra care should be taken with sensitive or confidential information and a secure paper destruction service bin used. Digital data will be destroyed by deleting or overwriting information and destroying the physical media, such as CD rom.

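### The supplementary logistic regression of 6-month diabetes on early or late-night mealtime is likely to have very few cases, and the plan names no small-sample method and no limit on how a null result may be read

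*Combined protocol and SAP*

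**What the plan says.** The Statistical Analysis section first relates night meal pattern to HbA1c, fasting glucose, 2-hour glucose and the CGM profile with a multivariable generalized linear model. It then adds a categorical analysis: "the glycemic outcome will be categorized into diabetes incidence (diabetes and non-diabetes) to determine the participants who had been diagnosed with diabetes at 6 months". The method follows: "A logistic regression test will be used to examine the association between early and late-night mealtime and diabetes incidence". No penalised or exact method is named, and no covariates, case count or power are given for this model. The same two-level outcome is used in a second logistic regression, on anthropometric status.

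On numbers, Sample size Calculation concludes with "a total of 83 prediabetic adults expected in this study" and raises this to 166 for 50% dropout; the synopsis gives 120. The calculation is for a single linear regression coefficient, not for a logistic model. The only progression rate in the document is background, in section 1.1: "Without appropriate interventions, 5.8%-18.3% of people with prediabetes develop diabetes yearly". Follow-up for this outcome is six months.

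**The concern.** Everyone enters with prediabetes and is followed for only six months, so few can be expected to reach diabetes. Maximum-likelihood logistic regression does poorly with a handful of cases. If one mealtime group has none, the estimated odds ratio is zero or infinite. If each group has one or two, the estimate is finite but very imprecise, and each added covariate makes it worse.

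The Introduction presents the study as a route to preventing progression to type 2 diabetes, and this is the only planned analysis of mealtime against progression itself. Without a caution in the plan, a non-significant result could be reported as evidence that late meals do not affect progression, although the analysis had little chance of showing an effect.

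**Working it through.** **Plan's own figure.** For a single coefficient in a fixed linear model, take 0.13 as f². The noncentrality is √(0.13 × 83) = 3.28, and two-sided power at 0.05 is 90.07%, so 83 reproduces. Dropout: 83 / (1 − 0.5) = 166. None of this concerns the logistic model.

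**Expected cases (assuming the section 1.1 rates).** Six-month risk is 1 − (1 − r)^0.5:
- r = 5.8%: 2.9%
- r = 18.3%: 9.6%

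| Number followed | Where from | Cases, low to high rate |
|---|---|---|
| 60 | synopsis 120, half lost | 1.8 to 5.8 |
| 83 | planned completers | 2.4 to 8.0 |
| 120 | synopsis, none lost | 3.5 to 11.5 |
| 166 | recruited, none lost | 4.9 to 16.0 |

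**Chance of an empty mealtime group.** The documents give no early/late split, so assume 41 late and 42 early, with a true odds ratio of 2 and overall risk as above. The chance is (1 − p_early)^42 + (1 − p_late)^41 minus their product.
- Low rate: p_early 2.0%, p_late 3.9%; 0.430 + 0.196 − 0.084 = 0.54.
- High rate: p_early 6.7%, p_late 12.5%; 0.055 + 0.004 − 0.000 = 0.06.

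At the low rate, the 54% includes about 8% of studies with no case in either group.

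**Power.** Exact enumeration of Fisher's two-sided test at 0.05, odds ratio 3, near-even split:

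| Number followed | Power, low to high rate |
|---|---|
| 60 | 0.1% to 7% |
| 83 | 2% to 24% |
| 120 | 2% to 26% |
| 166 | 6% to 41% |

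**Uneven split.** With 30 late and 53 early at N = 83, odds ratio 3 means risks of 1.7% early and 5.0% late (low rate) or 6.0% and 16.0% (high rate). The same enumeration gives 8% and 25%, so the conclusion does not depend on an even split.

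**Covariates.** If the six confounder domains listed for the generalized linear model were added at one parameter each, the seven parameters would have 2.4 / 7 ≈ 0.3 to 8.0 / 7 ≈ 1.1 cases apiece.

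**A three-level outcome (normal, prediabetes, diabetes).** Whitehead's proportional-odds formula, V = n(1 − Σp³)/12, n = 83, odds ratio 3. The recovery rate is in neither the protocol nor the SAP text, so it is varied:

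| Assumed recovery | Power, low to high rate |
|---|---|
| none (yes/no outcome) | 13% to 31% |
| 5% | 27% to 43% |
| 10% | 39% to 52% |
| 20% to 40% | 56% to 74% |

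**The case against.** The strongest reply is about scope. Diabetes incidence is not among the main or secondary outcomes in the synopsis or under Study Outcomes, and the Statistical Analysis section introduces it as an addition. Mealtime is already related to continuous glycaemic measures. This stands, and it limits the point to a supplementary analysis.

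A reader might infer more in four ways, and the documents do not support any of them.
- **That coding diabetes yes/no throws away the contrast that motivates the study.** The Introduction does contrast people who progress with others: "some of the prediabetes cases showed tremendous improvement in their blood sugar result". But that contrast is in blood glucose, and the continuous outcomes keep it. Grouping normal with unchanged prediabetes is also simply what incidence of diabetes means.
- **That the plan itself predicts 2 to 8 cases.** The rates are a literature figure for people without appropriate interventions and are never used as a design assumption. Participants receive routine treatment, so the true count could be lower; differences in how diabetes is defined could move it either way.
- **That four or fewer cases can never reach significance.** With all cases late and 41 late eaters, Fisher's p at four cases is 0.055. With 35 late eaters it is 0.028, and with 30 late eaters three cases give 0.044. The plan explores cut-offs at 2000, 2100 and 2200 hours, so the split may well be uneven.
- **That an ordinal model should replace the binary one.** Its gain rests on an unknown recovery rate, it assumes one odds ratio for recovery and for progression, and it stays below 80% power at 83 participants throughout the range shown. The OGTT and HbA1c tables classify separately, with no rule for discordant results.

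It is also fair that at the high rate an empty group is unlikely (6%); there the trouble is imprecision and low power. And where neither group has a case, no method can estimate an effect on diabetes.

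**Conclusion.** The concern holds for the supplementary analysis of diabetes incidence. If the quoted background rates apply, the model as written could return no finite odds ratio in about half of studies at the low rate. Across both rates it would have little power even for an odds ratio of 3. Following all 166 recruits would not rescue it. The result rests on three assumptions not fixed by the plan: that the section 1.1 rates apply, that risk accrues evenly over the year, and the mealtime split. That maximum likelihood is intended is inferred from the absence of any other named method. The continuous-outcome analyses of mealtime are untouched, and the yes/no outcome is a legitimate question. This is a cheap improvement to a secondary piece of the plan, not a flaw in its main analysis.

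**What to change.** In the Statistical Analysis section:
- Report diabetes cases as counts and denominators by mealtime group.
- Give a Firth-penalised or exact odds ratio with its confidence interval, and adjust for at most one covariate, named in advance.
- Label the analysis exploratory and state that non-significance is not evidence of no association.
- Treat the anthropometry logistic regression, which uses the same outcome, in the same way.

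An ordinal model of normal, prediabetes and diabetes may be added as an optional supplement, once a rule for discordant OGTT and HbA1c results is written. It should not replace the binary outcome.

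The cost is a few sentences and possibly other software, since the named SPSS version 20 may not fit the penalised model. Timing also matters: the document is dated 6 May 2024, and the research schedule ends third visits on 06/03/2024 and starts data entry and analysis on 07/03/2024. If outcomes have already been seen, the change should be declared as post hoc.

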pattern from the validated questionnaires PSIQ and light exposure from the validated questionnaire HLEQ.

Statistical Analysis

All data will be performed statistical analysis using the SPSS software version 20 (SPSS Inc., Chicago, IL, USA). The socio-demographic will be presented as mean, standard deviations, median, interquartile range, frequency, and percentage. Data cleaning will be performed to exclude the outlier data before the normality is checked using Kolmogorov-Smirnov Test. The investigator considered $p < 0.05$ to be statistically significant. Chronotype, sleep quality, and light exposure will be analyzed as categorical variables whereas dietary intake, chrononutrition, anthropometry, glycemic measure, and physical activity will be analyzed as continuous variables.

The investigator will perform a multivariable generalized linear model to examine the association between night meal pattern (last night mealtime either dinner or supper with calories intake, frequency of night snacking, and the total number of the night snacking) and glycemic outcome (HbA1c, FPG, 2hPPG, CGM profile) by adjusting for the potential covariates. Specifically, nighttime will be characterized by the time range from 1900 and 0659 hours based on Malaysia solar time. The investigator will explore the late-night meal timing in 2000, 2100, and 2200 to examine its association with glycemic outcomes. The potential confounders include sociodemographic characteristics, physical activity, sleep pattern, sedentary behavior, diet quality, and light exposure will be controlled. ANCOVA test will be performed to understand the association between chrononutrition (breakfast skipping, meal frequency, eating window, sleep timing, chronotype, and fasting pattern) with glycemic variables, controlling for potential covariates (sociodemographic characteristics, light exposure, diet quality, physical activity and sleep pattern).

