422 Select "I do not eat lunch" if you do not typically eat lunch.
423 _____ A.M./P.M. _____ I do not eat lunch.
424
425 C4. What time is your last eating event before bed?
426 Please indicate A.M./P.M. as part of your response.
427 _____ A.M./P.M.
428
429 C5. What time do you fall asleep?
430 Please indicate A.M./P.M. as part of your response.
431 _____ A.M./P.M.
432
433 On average, on a typical weekend day or free day,
434
435 D1. What time do you wake up?
436 Please indicate A.M./P.M. as part of your response.
437 _____ A.M./P.M.
438
439 D2. What time is your first eating event of the day?
440 Please indicate A.M./P.M. as part of your response.
441 _____ A.M./P.M.
442
443 D3. What time do you eat lunch? Please indicate A.M./P.M. as part of your response.
444 Select "I do not eat lunch" if you do not typically eat lunch.
445 _____ A.M./P.M.
446 _____ I do not eat lunch.
447
448 D4. What time is your last eating event of the day before bed?
449 Please indicate A.M./P.M. as part of your response.
450 _____ A.M./P.M.
451
452 D5. What time do you fall asleep?
453 Please indicate A.M./P.M. as part of your response.
454 _____ A.M./P.M.
455
456 Reference:
457 Allison C. Veronda, Kelly C. Allison, Ross D. Crosby, and Leah A. Irish. 2019. Development, validation and
458 reliability of Chrononutrition Profile Questionnaire. Chronobiology International. DOI:
459 10.1080/07420528.2019.1692349
460
461
462
463
464

Anthropometry

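### The diabetes-incidence model enters last mealtime only as early versus late, with no cut defined, although it is recorded as a clock time

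*Combined protocol and SAP*

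**What the plan says.** The Hypothesis names two exposures, morning chronotype and early meal timing. Meal timing is measured on a clock: Appendix I asks "What time is your last eating event before bed" for workdays (item C4), with a matching item for free days (D4), and the food diary records the time of each item.

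Three statements in Statistical Analysis (section 3) bear on how that variable is used:

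- General rule: "dietary intake, chrononutrition, anthropometry, glycemic measure, and physical activity will be analyzed as continuous variables".
- Glycaemic outcomes: a multivariable generalized linear model on the night meal pattern, of which last mealtime (dinner or supper) is a part. Then: "The investigator will explore the late-night meal timing in 2000, 2100, and 2200 to examine its association with glycemic outcomes". Neither statement gives the coding of mealtime.
- Diabetes at 6 months: "A logistic regression test will be used to examine the association between early and late-night mealtime and diabetes incidence". No clock time for the boundary is given.

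The Sample size Calculation is for a "Linear Multiple Regression Fixed Model, single regression coefficient", with "Effect Size (β -coefficient): 0.13", "α Error prob: 0.05", "Power(1- β err prob): 0.90" and two tails. It gives 83 evaluable participants, or 166 after 50% dropout. No power is stated for the logistic model.

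**The concern.** In the incidence model, one of the two hypothesised exposures is reduced to two groups although the finer measurement is in hand. With a boundary at 20:00, for example, a last meal at 20:05 and one at 23:30 count as the same exposure, while 19:55 and 20:05 count as opposites. This departs from the plan's own rule that chrononutrition is continuous.

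Three things are at stake. A real association is more easily missed. A two-group contrast cannot show at what hour risk changes, although finding the optimal meal timing is a stated aim. And because no boundary is written down, while three candidate clock times appear in the preceding analysis, the cut could be settled after results are known. That last risk is not quantified here.

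**Working it through.** **1. Reproduce the plan's figure.** Inputs from Sample size Calculation: effect size 0.13, two-sided alpha 0.05, power 0.90. For one regression coefficient, the noncentrality is sqrt(f² × N) with N − 2 degrees of freedom for one predictor. With f² = 0.13 and N = 83 it is sqrt(10.79) = 3.28, df = 81, and power is 0.901. So 83 reproduces when 0.13 is read as Cohen's f², and 83/(1 − 0.5) = 166. If 0.13 were a standardised coefficient, power at 83 would be only 0.219.

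**2. Effect of one cut, linear model, N = 83.** Assume a roughly normal mealtime, a linear effect, and 0.13 as the f² of continuous mealtime. Then R² = 0.13/1.13 = 0.115. Calling a share p late multiplies R² by k = φ(z_p)²/[p(1 − p)]. For p = 0.5, k = 0.3989²/0.25 = 0.637, R² = 0.0732, f² = 0.0732/0.9268 = 0.079, and power is 0.716. The documents do not give the share of late eaters, so a range is shown.

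| Share late | k | Power (uncut 0.901) | Loss, points | N for 0.90 |
|---|---|---|---|---|
| 50% | 0.637 | 0.716 | 18.5 | 135 |
| 30% | 0.576 | 0.669 | 23.2 | 151 |
| 20% | 0.490 | 0.595 | 30.6 | 178 |
| 15% | 0.426 | 0.534 | 36.7 | 206 |

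**3. Dependence on the number analysed.** The summary table gives 120 participants, and Sample size Calculation gives 166 recruits. Taking 60 as 120 after 50% dropout:

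| N analysed | Uncut | 50/50 | 15/85 | Loss, points |
|---|---|---|---|---|
| 60 | 0.784 | 0.572 | 0.409 | 21 to 38 |
| 83 | 0.901 | 0.716 | 0.534 | 18 to 37 |
| 120 | 0.975 | 0.863 | 0.694 | 11 to 28 |
| 166 | 0.996 | 0.950 | 0.829 | 5 to 17 |

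**4. If 0.13 is already the effect of a cut exposure.** The cut analysis then keeps 0.90 at N = 83. Continuous mealtime would have R² = 0.115/0.637 = 0.181 (50/50) to 0.115/0.426 = 0.270 (15/85), with power 0.99 to 1.00. The cut costs about 9 to 10 points.

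**5. The logistic model itself.** Section 1.1 (Prediabetes) quotes yearly progression of 5.8% to 18.3%. Half of each is 2.9% and 9.15%, which is 83 × 0.029 = 2.4 to 83 × 0.0915 = 7.6 events. Simulated power (likelihood-ratio test, normal exposure, assumed odds ratio 2.0 to 2.5 per SD later, 50% or 20% late):

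| 6-month rate | Continuous | Early/late |
|---|---|---|
| 9.15% | 0.42 to 0.60 | 0.29 to 0.43 |
| 2.9% | 0.20 to 0.27 | 0.12 to 0.19 |

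With odds ratios down to 1.5 per SD, power with continuous mealtime runs from about 0.08 to 0.64, and the loss from cutting from about none to 20 points. With so few events these figures are approximate.

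**The case against.** The strongest case on the other side has five parts.

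- **The linear figures may start from the wrong baseline.** Section 3.1.1 of the literature review describes the cohort behind the 0.13 as relating dinner after 8 pm to HbA1c, so 0.13 may already be a cut effect. This stands as a real possibility. The loss on the linear sizing is then 9 to 10 points, and the cut analysis keeps its 0.90.
- **The sizing is not for this model.** A reader might infer that the incidence analysis falls 18 to 37 points short of a promised 90%. It does not: the 90% belongs to a linear coefficient, and the plan claims no power for the logistic test.
- **The glycaemic outcomes are not shown to be cut.** A reader might take 20:00, 21:00 and 22:00 as replacing the continuous analysis of HbA1c, fasting glucose, 2-hour glucose and CGM. The text does not support that. The main model includes last mealtime, the general rule makes it continuous, and the clock times are only to be explored. What remains is that the coding is not stated.
- **Importance.** Mealtime is not labelled the main exposure; the hypothesis gives it equal place with chronotype. Diabetes incidence is not among the listed main or secondary outcomes. Both points stand and limit the weight of the finding.
- **Linearity.** If risk truly steps up at a clock time, a straight line also loses information: 1 − 0.637 = 0.363 of it for a step at the median. This is a reason to check the shape, not to leave the cut undefined.

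The 8 pm description gives 20:00 some background, but Statistical Analysis does not invoke it, and it does not bear on 21:00 or 22:00.

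**Conclusion.** The point holds for the diabetes-incidence model. As worded, that model uses an early/late contrast with no stated boundary, against the plan's own rule and despite recorded clock times. The cost there is about none to 20 points of power with 83 participants, assuming a roughly normal mealtime, a roughly linear effect, the background event rates in section 1.1 and odds ratios of 1.5 to 2.5 per SD. Power is low with or without the split, so the loss of shape and the open choice of cut matter at least as much as the lost power.

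The drop from 0.90 to between 0.72 and 0.53 is an illustration on the plan's linear sizing. It is conditional on N = 83, on 0.13 being the f² of continuous mealtime, and on splits from 50/50 to 15/85. It is smaller at larger N or if 0.13 is already a cut effect. For the glycaemic outcomes the finding is limited to unstated coding.

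**What to change.** **Incidence model.** Enter last mealtime in hours, with times after midnight coded as 24:00 plus, and report the odds ratio per hour later. Use the same source and definition of last mealtime as the glycaemic model. The plan must name that source, because the glycaemic text refers to dinner or supper with its calories while Appendix I records any last eating event on workdays and free days. Keep any early/late split as a secondary analysis with one cut written down before the data are examined.

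**Glycaemic model.** State that last mealtime enters the generalized linear model in hours, following the plan's rule for chrononutrition. Add one pre-specified 3-knot restricted cubic spline to check for a threshold. Report model-predicted glycaemia at 20:00, 21:00 and 22:00.

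**Cost.** A few sentences in Statistical Analysis and one decision on the source; no new data or participants. A per-hour slope is less direct for advice than a single clock time and fits a true step less well. The predicted values and the spline address this for the glycaemic outcomes, and the secondary split gives a two-group contrast for incidence.
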